9.8.2.2 Gene Expression Analyses

Exploratory analyses of messenger RNA (and/or miRNA) will be completed using total RNA isolated from fresh tumor tissue (processed in RNA later). RNA-sequencing, microarrays, and/or similar methodologies, including but not limited to quantitative real time polymerase chain reaction (PCR), will be used to assess gene expression patterns associated with RCC and to identify changes in those gene expression patterns following treatment with each FRACTION-RCC study treatment combination and/or nivolumab in combination with ipilimumab, where applicable. Ultimately, this approach may lead to the identification of unique baseline or On-treatment RNA expression signatures that can be useful for identifying participants who are likely (or unlikely) to respond to treatment with a given FRACTION-RCC study treatment combination. Focus may be given to monitoring a battery of immunoregulatory genes associated with cancer cells or cancer-interacting lymphocytes. Examples within the latter group include genes associated with T-cells, NK cells, and/or IFN γ signaling. Such genes have been implicated previously in tumor responses.

9.8.2.3 Protein Expression and Mutation

A portion of the fresh biopsy specimen will be formalin fixed, paraffin embedded (FFPE), and analyzed by IHC to determine the abundance of immunoregulatory proteins present at the tumor site. Such analyses may reflect the presence of tumor-infiltrating immune cells or the expression of immunoregulatory proteins by the tumor and/or surrounding stroma. Analytes may include, but are not limited to, CD3, CD4, CD8, FoxP3, GITR, GITR ligand, PD-L1, and components of antigen presentation machinery (beta-2 microglobulin, major histocompatibility complex [MHC] Class I, and MHC Class II).

Pharmacodynamic changes in the presence or abundance of immunoregulatory proteins and other proteins will be sought. Baseline and pharmacodynamic measures may also be correlated with clinical outcomes.

Laser capture microdissection may be utilized to enrich specific regions of tumor material for use in similar or additional downstream applications. This enrichment may provide robust signals of immunomodulation that are not otherwise detectable when tumor material is prepared using conventional methods. Downstream applications may include, but are not limited to, cytometry, ELISA, and/or assessment of miRNA, and gene expression. This process may be used to corroborate potentially weak signals observed by standard IHC, RNA, and/or miRNA expression experiments described above.

Tumor tissue may also be used to investigate receptor occupancy and for proteomic analysis or other exploratory analysis of protein expression and characterization.

T-cell receptor sequencing of T-cells derived from the tumor may be evaluated for association with clinical response and to understand pharmacodynamic changes.

Lastly, DNA may be extracted from a portion of tumor material to monitor somatic mutations that may impact response and other efficacy measures. Tumor mutational load has been associated with response to immunomodulatory agents, including nivolumab.⁶⁰

9.8.3 Tissue Markers from Archived Tumor Samples

In addition to fresh tumor biopsy (see [Section 9.8.2](#)), an archival FFPE tumor tissue block (preferred) or slide (minimum of 20 slides) samples from a primary or metastatic site are to be provided by all participants, if available. Molecular characterization of archival specimens will be similar to the characterizations described above but is likely to focus on the expression of candidate markers associated with response to FRACTION-RCC study treatment combination. As described above, DNA may be extracted from a portion of the tumor material for mutational analysis. Lastly, RNA may be quantified from archival specimens using in situ hybridization, real-time PCR, or similar methodologies. Comparing protein expression, RNA expression, and mutation profiles in archival versus fresh specimens may provide insights into the molecular basis for disease progression.

9.8.4 Additional Research Collection

Additional research collections are mandatory for all participants, except where prohibited by local laws and regulations or where specific waiver is provided by the BMS Medical Monitor (or designee); if one of these exceptions occur, participation in additional research collection should be encouraged but will not be a condition of overall study participation.

This protocol will include residual sample storage for additional research. Samples to be included are peripheral blood samples for PK, immunogenicity, and biomarker analysis (including derived material), and tumor tissue.

This collection for additional research is intended to expand the translational research and development capability at BMS and will support as yet undefined research aims that will advance our understanding of disease and options for treatment. It may also be used to support health authority requests for analysis and advancement of pharmacodiagnostic development to better target drugs to the right patients. This may also include genetic/genomic exploration aimed at exploring disease pathways, progression, response to treatment, etc.

All requests for access to samples or data for additional research will be vetted through a diverse committee of the Sponsor's senior leaders in Research and Development to ensure the research supports appropriate and well-defined scientific research activities.

All residual blood and tissue samples will be retained by the BMS Biorepository for additional research purposes.

Samples will be securely stored by the BMS Biorepository in Hopewell, NJ or at a BMS-approved third-party storage management facility.

Samples will be stored in a coded fashion, and no researcher will have access to the key. The key is securely held by the investigator at the clinical site, so there is no direct ability for a researcher to connect a sample to a specific individual.

Additional research samples will be retained for 15 years or the maximum allowed by applicable law. No additional sampling is required for residual collections.

Further details of sample collection and processing will be provided to the site in the procedure manual.

9.8.5 Immunogenicity Assessments

Separate detailed instructions for the collection, processing, handling, labeling, storage, and shipment of PK and immunogenicity samples will be provided in the Laboratory Procedures Manual.

The details pertaining to the timing of immunogenicity sample collection for the On-treatment Phase and Follow-up are provided in each FRACTION-RCC Sub-Protocol.

The serum samples will be banked for analyses of ADAs by validated immunoassays. In addition, selected serum samples may be analyzed by an exploratory method that detects ADAs for technology exploration purposes; exploratory results will not be reported. Serum samples

designated for PK or biomarker assessments may also be used for immunogenicity analysis, if required (eg, insufficient volume for complete immunogenicity assessment or to follow up on suspected immunogenicity-related AE).

9.8.6 RNA Transcriptome Research

See [Section 9.8.2.2](#).

9.8.7 RNA Expression Research of a Subset of RNA Species

Not applicable.

9.8.8 Proteome Research

See [Sections 9.8.1.3](#) and [9.8.2.1](#).

9.8.9 Metabolomic Research

Not applicable.

9.8.10 Other Assessments

Not applicable.

9.9 Medical Resource Utilization and Health Economics

Not applicable.

10 STATISTICAL CONSIDERATIONS

Additional statistical considerations may be provided in each subprotocol. Please refer to the specific sub-protocol for guidance.

10.1 Sample Size Determination

Sample sizes are guided by Simon 2-stage (optimal) designs. Because of the different participant populations (anti-PD-1, anti-PD-L1, and anti-CTLA-4 treatment-naïve versus anti-PD-1, anti-PD-L1, or anti-CTLA-4 treatment-experienced) and existing care options under each Track, different criteria are applied to determine the number of participants for each stage and the strength of the efficacy signal that would recommend proceeding to the next stage. Details are described in subsequent sections and in [Table 10.1-1](#).

For sample size calculation and for simplicity of description, recommendations for stopping or progressing to the next stage are based on the number of objective responses observed. However, since best overall response (BOR) does not necessarily capture the full extent of clinical benefit and since response can be delayed or of short duration, the BMS Medical Monitor (or designee) will also review other aspects of clinical benefit that may better predict OS benefit, such as DOR and PFSR, as well as the relative performance of different study treatment combination arms, before making a final determination.

Enrollment may continue after reaching the indicated number of participants at Stage 1 while the initial efficacy evaluation is ongoing. Additional participants may be enrolled to account for participants who may drop out of the study without being evaluable for response or for additional considerations that may be needed in Stage 2 such as PK/PD analyses. In such cases, the total

number of participants enrolled will not exceed the specified total number of participants treated in that arm according to Simon 2 stage. Although the sample size calculations are based on efficacy considerations, safety will also be continuously assessed and will be taken into account in the decision to continue or terminate a study treatment arm. In Track 2, 41 participants per study treatment arm in Stages 1 and 2 combined will result in 88% probability of detecting an AE that has a true rate of 5%. More participants per study treatment arm in Stages 1 and 2 combined will result in a higher probability of detecting an AE that has a true rate of 5%.

Table 10.1-1: Simon 2-Stage (Optimal) Design Consideration

Track	Historical ORR/Target ORR	Stage 1 Responders/Stage 1 n		Stage 2 Responders/Total n		Expected n with Historical ORR	Expected n with Target ORR
		Consider Futility	Go to Stage 2	Consider Futility	Consider Efficacy		
1	30% / 50%	$\leq 8/24$	$\geq 9/24$	$\leq 24/63$	$\geq 25/63$	34.5	60.0
2	5% / 20%	$\leq 1/21$	$\geq 2/21$	$\leq 4/41$	$\geq 5/41$	26.6	39.8

Note: Numbers of responses serve as a guideline; however, the totality of efficacy data will be considered when making decisions to terminate or continue an arm.

The Track 1 Simon 2-stage (optimal) design assumes a historical response rate of 30% and a target response rate of 50%, based on the observed response rate of approximately 40% for the nivolumab and ipilimumab combination in Study CA209016 and approximately 25% for nivolumab monotherapy in Study CA209025. A false positive rate of 5% and power of 90% are used.

[figure not shown]
Because there is very little data available on participants with prior anti-PD-1, anti-PD-L1, or anti-CTLA-4 treatment, the Track 2 design is not based on an observed historical response rate. Rather, the assumption is made that a response rate below 5% would not be worth further study and that a target response rate of 20% would be worth pursuing in this population. A false positive rate of 5% and power of 90% are used. With regard to sample size, participants who are re-randomized to a different study treatment in Track 2 will be counted once for each randomization; participants who are retreated within the same study treatment arm will only be counted once.

10.1.1 Track 1 - Anti-PD-1, Anti-PD-L1, and Anti-CTLA-4 Treatment-naïve

As shown in [Table 10.1-1](#), a minimum of 24 participants in each study treatment combination arm will be treated in Stage 1 for an initial evaluation of efficacy. If the number of responses observed in Stage 1 is $\leq 8/24$, the study treatment combination arm would likely not be considered efficacious; otherwise, enrollment to Stage 2 will continue, and an additional 39 participants will be treated. If the total number of responses at the end of Stage 2 is $\leq 24/63$, the study treatment arm will be terminated for futility; if there are more than 24 responses observed at the end of Stage 2, the study treatment combination may be carried on for further treatment development. The totality of efficacy data and response profile for each combination will be considered when making decisions to terminate or continue an arm.

The operating characteristics of this Simon 2-stage (optimal) design are provided in [Figure 10.1.1-1](#). With the stopping boundaries as shown in [Table 10.1-1](#), if the combination has an ORR no better than the historical control at 30%, then there is a 95% overall chance of stopping for futility, with a 73% chance of stopping at Stage 1; there is a 5% false positive rate. If the combination has an ORR equal to the target of 50%, then there is a 90% chance of stopping for efficacy after Stage 2, whereas if the true ORR is 35%, 40%, or 45%, the power would be 20%, 48%, or 74%, respectively.

Figure 10.1.1-1: Operating Characteristics of Track 1 Simon 2-stage (Optimal) Design (Power =90%, Alpha = 5%)

Abbreviation: ORR = overall response rate; prob = probability.

If 25 responses are observed at the end of Stage 2 (Efficacy Stop), then the 90% CI for ORR will be [29%, 51%]. The CI is calculated using the Clopper-Pearson method.

As stated in [Section 10.1](#), the number of responses given here is used for sample size calculation and for simplicity of description. Before making a decision to terminate or continue an arm, BMS will also review the totality of all available data, which includes: other aspects of efficacy that may help predict OS benefit, such as DOR and PFSR; clinical safety information; and biomarker data; as well as the relative performance of other treatment arms.

[figure not shown]
10.1.2 Track 2 - Anti-PD-1, Anti-PD-L1, or Anti-CTLA-4 Treatment-experienced Participants

For each study treatment combination arm under Track 2, the Simon 2-stage (optimal) design will be used. Initially, 21 participants per study treatment combination arm will be treated in Stage 1, and preliminary efficacy will be assessed when those participants are evaluable. If 1 or fewer responses are observed in Stage 1, the study treatment arm would likely not be considered efficacious; otherwise, Stage 2 will be initiated and enroll an additional 20 participants, for a total of 41 participants per study treatment combination arm. The totality of efficacy data and response profile for each combination will be considered when making decisions to terminate or continue an arm.

The operating characteristics of this Simon 2-stage (optimal) design are provided in [Figure 10.1.2-1](#). With the stopping boundaries as shown in [Table 10.1-1](#), if the combination has an ORR no better

than 5%, then there is a 95% overall chance of stopping for futility, with a 72% chance of stopping at Stage 1; there is a 5% false positive rate. If the combination has an ORR equal to the target of 20%, then it has a 90% chance of stopping for efficacy after Stage 2.

Figure 10.1.2-1: Operating Characteristics of Track 2 Simon 2-stage (Optimal) Design (Power =90%, Alpha = 5%)

Abbreviation: prob = probability.

If 5 responses are observed at the end of Stage 2 (Efficacy Stop), then the 90% CI for ORR will be [5%, 24%]. The CI is calculated using the Clopper-Pearson method.

As stated in [Section 10.1](#), the number of responses given here is used for sample size calculation and for simplicity of description. Before making a decision to terminate or continue an arm, BMS will also review the totality of all available data, which includes: other aspects of efficacy that may help predict OS benefit, such as DOR and PFSR; clinical safety information; and biomarker data; as well as the relative performance of other treatment arms.

Both participants previously treated in any Track (re-randomized participants) and new participants who meet eligibility criteria are permitted to enter Track 2. Some slots in Track 2 will be reserved for re-randomized participants to ensure that both types of participants are enrolled in Track 2. At the initiation of the study, recruitment of re-randomized participants will be limited to 11 participants per Track 2 study treatment combination arm in Stage 1 (with 25% dropout rate considered). In Stage 2, recruitment of additional re-randomized participants will be limited to 12 participants out of the 27 additional participants (with 25% dropout rate considered). The limited number of re-randomized participants may be re-adjusted depending on the enrollment

rates, the rate of progression in Tracks 1 and 2, and the number of currently open study treatment arms in Track 2.

10.1.3 Tracks 1 and 2 Pharmacodynamic/Biomarker Assessment

To assess the pharmacodynamic effects of FRACTION-RCC combination or nivolumab in combination with ipilimumab as stated in the exploratory objective, pretreatment and On-treatment whole blood, serum samples, and tumor biopsies will be required. It is of interest to ensure the precision of the estimate of the ratio of On-treatment biomarker assessments to pretreatment (baseline) levels. Assuming that a biomarker is measured as a continuous variable with log-normal distribution, a given number of participants per study treatment arm under different Track will provide the confidence that the estimate of the ratio of On-treatment to baseline values will be within 20% of the true value, as shown in Table 10.1.3-1.

Table 10.1.3-1: Probability That Estimated Ratio of On-treatment to Pretreatment (Baseline) Value Is Within 20% of True Value

Intra-participant Standard Deviation (Log-scale)		0.2	0.3	0.4	0.5	0.6	0.7	0.8
Probability	N = 21	100%	97%	89%	81%	72%	65%	59%
	N = 24	100%	98%	92%	84%	75%	68%	62%
	N = 41	100%	100%	97%	93%	87%	81%	75%
	N = 63	100%	100%	99%	97%	94%	89%	84%

Abbreviations: N = number of participants.

For example, for a biomarker (eg, activated and memory CD4 and CD8 T-cells) with an intra-participant standard deviation of 0.5, if the true ratio of postbaseline to baseline geometric means is 1.2 (increase from baseline is 20%), there is 93% probability that the estimated ratio would be within 0.96 and 1.44 (or a percent change between -4% and 44%) with 41 participants per study treatment arm. If the true increase from baseline is 60%, for a biomarker with the same variability, then there is 93% probability that the estimated percent change would be between 28% and 92% with 41 participants per study treatment arm.

10.2 Populations for Analyses

For purposes of analysis, the following populations are defined:

Table 10.2-1: Populations for Analyses

Population	Description
Enrolled	All participants who sign informed consent
Randomized	All participants who are randomized to any study treatment arm of any Track in this study.
Treated	All participants who are randomized and take at least 1 dose of study treatment

Table 10.2-1: Populations for Analyses

Population	Description
PK	All treated participants who have evaluable concentration-time data
Immunogenicity	All treated participants who have available immunogenicity assessment data
Biomarker	All treated participants who have available biomarker data
Response-evaluable	All treated participants with measurable disease and one of the following: 1) at least 1 postbaseline tumor measurement, 2) clinical progression, or 3) death.

10.3 Statistical Analyses

The statistical analysis plan will be developed and finalized before database lock. Below is a summary of planned statistical analyses of the primary and secondary endpoints.

10.3.1 Efficacy Analyses

The primary efficacy analyses will be performed on the treated population for the final analysis. Efficacy analyses based on the response-evaluable population may be performed for interim analyses when the minimum follow-up period is less than sufficient to warrant adequate interpretation of the result. Details on censoring scheme on time-to-event endpoints such as DOR, progression-free survival (PFS), and OS will be described in the statistical analysis plan.

Table 10.3.1-1: Efficacy Analyses

Endpoint	Statistical Analysis Methods
ORR BOR for a participant will be assessed per RECIST v1.1 by investigator.	Estimate of ORR and corresponding 2-sided exact 95% CI using the Clopper-Pearson method by study treatment under each Track.
Median DOR DOR for a participant with a BOR of CR or PR is defined as the time between the date of first response and the date of the first objectively documented tumor progression per RECIST v1.1 or death, whichever occurs first.	Median DOR using the Kaplan-Meier method and corresponding 2-sided 95% CI using Brookmeyer and Crowley methodology (using log-log transformation) by study treatment under each Track.
PFSR at 24 weeks PFS for a participant is defined as the time from the first dosing date to the date of first objectively documented disease progression or death due to any cause, whichever occurs first.	Estimate by the Kaplan-Meier method and corresponding 95% CI will be derived based on Greenwood formula by study treatment under each Track.
OS rate at certain time points OS for a participant is defined as the time from the first dosing date to the date of death due to any cause.	Estimate by the Kaplan-Meier method and corresponding 95% CI will be derived based on Greenwood formula by study treatment under each Track.

Treatments under each Track for different populations will be analyzed independently. There is no intention to combine the same study treatment across Tracks for efficacy analyses.

Participants re-randomized into Track 2 will be combined with participants originally randomized into Track 2 for efficacy analysis.

Specific analyses to be performed for each Track are shown in Table 10.3.1-2.

Table 10.3.1-2: Analyses Planned for Each Track

Track		ORR	DOR	PFSR	OS
Track 1	End of Simon Stages 1 and 2	X	X	X	X
Track 2	End of Simon Stages 1 and 2	X	X	X	X
	Early Termination at Simon Stage 1			X	X

Abbreviations: DOR = duration of response; ORR = overall response rate; OS = overall survival; PFSR = progression free survival rate.

Track 1 - Anti-PD-1, Anti-PD-L1, and Anti-CTLA-4 Treatment-naïve Participants

The following additional analyses will be performed for Track 1 anti-PD-1, anti-PD-L1, and anti-CTLA-4 treatment-naïve participants at the end of Stage 2. These efficacy analyses will be performed when the study treatment arms have been fully enrolled and followed up for at least 6 months. A descriptive odds ratio and estimate of the difference in ORRs, along with corresponding 2-sided 95% CIs, will be provided to evaluate differences between the 2 randomized study treatment arms (FRACTION- RCC study treatment combination arm and nivolumab in combination with ipilimumab control arm). Additionally, for each study treatment arm, the ORR and corresponding 95% CIs will be calculated using Clopper-Pearson method. A descriptive hazard ratio and corresponding 2-sided 95% CI of PFS and OS will be estimated in a Cox proportional hazards model using study treatment as a single covariate to evaluate difference between the 2 study treatment arms (experimental and control arms). The PFS and OS curves for each study treatment arm will be estimated. Two-sided 95% CIs for median PFS and OS will be computed. PFSR at 24 weeks and survival rates at certain time points (eg, 2 years) will be estimated. Associated 2-sided 95% CIs will be calculated.

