2 SCHEDULE OF ACTIVITIES

Study assessments and procedures are presented in [Table 2-1](#) (Screening Procedural Outline), [Table 2-2](#) (Baseline for Re-randomization Procedural Outline) - Not applicable per Protocol Amendment 07, and [Table 2-3](#) (Follow-up Procedural Outline). The On-treatment Procedural Outline(s) and exceptions for study treatment combination arms are included in each Fast Real-time Assessment of Combination Therapy in Immuno-Oncology for renal cell carcinoma (FRACTION-RCC) Sub-Protocol.

In the event that multiple procedures are required at a single time point, the following is a list of procedures from highest priority to lowest:

- Safety (clinical laboratory examinations)
- Safety (electrocardiogram [ECG])
- Biomarker sampling
- Pharmacokinetic (PK) and anti-drug antibody (ADA) sampling

Table 2-1: Screening Procedural Outline

Procedure	Screening Visit ^a	Notes
Eligibility Assessments		
Informed Consent	X	A participant is considered enrolled only when a protocol-specific informed consent is signed. Obtain patient identification number via IRT after signing of the written informed consent.
Utilize IRT	X	Obtain patient identification number. After completing all screening procedures, utilize IRT to either screen fail or obtain randomization information, as applicable. Randomization can occur up to 5 - 7 days prior to first dose. In limited circumstances, if patients cannot be treated within 5 - 7 days of randomization due to a study-related test, the duration can be extended after discussion with the BMS Medical Monitor (or designee).
Inclusion/Exclusion Criteria	X	All inclusion/exclusion criteria should be assessed at screening and confirmed prior to first dose.
Medical History	X	Includes prior conditions and any toxicities or allergies related to previous treatments.
Collect Data on Prior Anti-PD-1, Anti-PD-L1, or Anti-CTLA-4 Treatment Exposure	X	Prior to screening for the protocol, investigative sites are required to determine the participant's exposure to anti-PD-1, anti-PD-L1, or anti-CTLA-4 treatment. Those data will be collected as part of the Screening Phase. Toxicities from prior immunotherapies with details on timing, treatment, and resolution, if applicable, should be captured.
Prior Therapy	X	Radiotherapy/surgery/systemic therapy administered for the treatment of RCC
Safety Assessments		

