4 OBJECTIVES AND ENDPOINTS

The overall FRACTION-RCC study-wide objectives are presented in the following sections. Any changes to these objectives for specific study treatments are specified in each FRACTION-RCC Sub-Protocol.

Table 4-1: Objectives and Endpoints

Objectives	Endpoints
Primary	
To assess the efficacy (ORR, DOR, and PFSR at 24 weeks) of each FRACTION-RCC study treatment combination (relative to nivolumab in combination with ipilimumab, when applicable) in participants with advanced RCC	ORR defined as the proportion of all treated participants with a BOR of CR or PR as assessed per RECIST v1.1 by investigator, median DOR, and PFSR at 24 weeks
Secondary	
To investigate additional safety and tolerability of each FRACTION-RCC study treatment combination in participants with advanced RCC	Incidence of AEs, SAEs, AEs leading to discontinuation, deaths, and clinical laboratory test abnormalities
Tertiary/Exploratory	

 To assess the pharmacodynamic effects as a function of exposure, by evaluation of select biomarkers in the peripheral blood and tumor biopsy specimens To explore potential associations between anti-tumor activity or safety and select biomarker measures in tumor biopsy specimens and peripheral blood prior to study treatment and following administration To evaluate the PK of each IP component To evaluate the immunogenicity of each IP, when applicable To assess the OS in treated participants To evaluate changes in disease-related symptoms, as measured by the FKSI-DRS, in treated participants 	
 Summary measures of change (or % change) from baseline or baseline level biomarker measurements in peripheral blood or tumor tissue Correlation (or similar appropriate measure of association) of biomarker measure in peripheral blood or tumor tissue with parameters of interest Summary measures of PK parameters from serum concentration. Incidence of ADAs OS rate at certain time points Summary measures of EQ-5D-3L index scores, VAS scores, FKSI-DRS scores, and corresponding change from baselines for each score

Table 4-1: Objectives and Endpoints

Objectives	Endpoints

 To evaluate general health, functional status, and utility for health using the EQ-5D-3L in treated participants 	

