6 STUDY POPULATION

For entry into the FRACTION-RCC study (per FRACTION-RCC Master Protocol), the following criteria MUST be met prior to dosing on Day 1. For entry into a study treatment per a FRACTION-RCC Sub-Protocol, additional treatment-specific criteria, if applicable, must also be met.

No exceptions will be granted.

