Section 2, Schedule of Activities; Table 2-2, Baseline for Re-randomization Procedural Outline; Section 3.1.1.2, Specific Attributes of the FRACTION Program Design; Section 5.1, Overall Design; Section 5.1.1, FRACTION-RCC Tracks 1 and 2 Design; Figure 5.1.1-1, Tracks 1 and 2 Study Design Schematic; Section 5.1.3.2, Treatment; Section 5.1.3.3, Follow-up; Section 5.4.1, Rationale for Duration of Therapy	Participants will receive treatment up to 2 years total duration.	Emerging data suggests that patients may derive clinical benefit beyond 6 months of immunotherapy. Therefore, patients will continue on study treatment for up to 2 years.
Table 2-1, Screening Procedural Outline	1. Duration of randomization prior to first dose extended	1. To allow patients to complete all the post randomization procedures required for a sub-protocol, duration between randomization and start of treatment can be extended from to allow for completion of study related tests.
	2. Data to be collected on toxicities from treatment with prior immunotherapies.	2. For patients previously treated with PD-1/PD-L1/CTLA-4, enrolling directly into Track 2, we will collect additional data on details of prior toxicities.
Table 2-3, Follow-up Procedural Outline	Karnofsky Performance Status assessment added at Follow-up visits 2 and 3	Collect performance status during follow-up.
Section 3.1, Introduction; Section 3.2.1, FRACTION-RCC	Included updates from recent clinical studies.	Most recent results of studies provided.
Throughout	Minor rewording/re-formatting for clarification.	Minor, therefore have not been summarized.

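### The descriptive Track 1 comparison with control leaves out randomised participants who were never dosed and starts PFS and OS at first dose, so loss before dosing that differs by arm could bias it in either direction

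*Combined protocol and SAP*

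**What the plan says.** - **Analysis set.** Section 10.3.1: "The primary efficacy analyses will be performed on the treated population for the final analysis". Table 10.2-1 defines that set as "All participants who are randomized and take at least 1 dose of study treatment". Table 4-1 matches it: "ORR defined as the proportion of all treated participants with a BOR of CR or PR".
- **Clock.** Table 10.3.1-1 measures PFS and OS from the first dosing date.
- **Comparison.** For Track 1 at the end of Stage 2, Section 10.3.1 plans a descriptive odds ratio and ORR difference "to evaluate differences between the 2 randomized study treatment arms", and descriptive Cox hazard ratios for PFS and OS. It names no separate set, so the treated set applies.
- **Randomised set.** Table 10.2-1 also defines "All participants who are randomized to any study treatment arm of any Track in this study", but Section 10.3.1 gives it no efficacy use.
- **Gap before dosing.** The study is open-label (Section 7.3). Table 2-1: "Randomization can occur up to 5 - 7 days prior to first dose". An extension is possible in limited circumstances, for a study-related test, after discussion with the medical monitor.
- **Undosed participants.** Section 9.2.1 sets 30 days of SAE collection for participants who are randomised and never treated. Section 6.4.1 lets a pretreatment failure re-enrol, and its wording covers someone randomised but not treated.

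**The concern.** Randomisation protects a comparison only if everyone allocated is kept in it. Here the assigned arm can be known before dosing, and a participant who leaves in that interval disappears from the odds ratio, the ORR difference and the hazard ratios. If leaving depends on the arm and on prognosis, the dosed groups are no longer exchangeable. Re-enrolment adds a second route: as written, a participant who is not dosed after one allocation could return, be randomised again and be counted only under the later arm. Starting the clock at first dose also hides any delay that differs by arm.

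The comparison has some weight. The primary objective in Section 4 assesses each combination relative to nivolumab plus ipilimumab where applicable, and Section 10.1.1 lists the relative performance of other arms among the data reviewed before an arm is stopped or continued.

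**Working it through.** **1. The plan's own figures.** No sample size or power is stated for the comparison, so the only Track 1 figures to reproduce are those of the Simon design (Section 10.1.1). Exact binomial calculation with boundaries 8/24 and 24/63:

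| Quantity | Stated | Recomputed |
|---|---|---|
| False positive rate at 30% | 5% | 0.0497 |
| Power at 50% | 90% | 0.903 |
| Stop at Stage 1 at 30% | 73% | 0.725 |
| Power at 35 / 40 / 45% | 20 / 48 / 74% | 0.206 / 0.478 / 0.743 |
| Expected n at 30% / 50% | 34.5 / 60.0 | 34.7 / 60.0 |

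These reproduce to rounding (24 + 39 × 0.27 = 34.5 with the rounded 73%). They are single-arm figures and are not in dispute.

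**2. Inputs for the comparison**
- Arm size: 63 per arm. Section 10.1 gives 63 for the experimental arm, and Section 7.2 sets the control cap equal to the largest experimental cap.
- p = 40% ORR in both arms had everyone been dosed. This is the approximate nivolumab plus ipilimumab rate in Section 10.1; equality of the arms is an assumption.
- d = undosed fraction, assumed 2% to 15% in the control arm only. The documents give no rate.
- q = ORR the undosed would have had, assumed 0% to 60%.

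**3. Shift in the ORR difference (experimental minus control)**

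Treated-set control ORR = (p − dq)/(1 − d). For d = 5%:
- q = 0: 0.40/0.95 = 42.1%, a shift of −2.1 points.
- q = 60%: (0.40 − 0.03)/0.95 = 38.9%, a shift of +1.1 points.

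If undosed participants are instead counted as non-responders, control ORR = p − dq and the shift is +dq.

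| d, control only | Shift, treated set | Shift, all randomised, undosed as non-responders |
|---|---|---|
| 2% | −0.8 to +0.4 | 0 to +1.2 |
| 5% | −2.1 to +1.1 | 0 to +3.0 |
| 10% | −4.4 to +2.2 | 0 to +6.0 |
| 15% | −7.1 to +3.5 | 0 to +9.0 |

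The treated-set shift is zero if the undosed fraction and prognosis match between arms. The last column answers a different question, response under the arm assigned, so it can also move away from the difference had all been dosed. That is why the two results belong side by side.

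**4. Scale.** The 95% CI half-width for the ORR difference at 63 per arm and 40% is 1.96 × √(2 × 0.4 × 0.6/63) = 17.1 points.

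**5. Effect on one arm's rate.** With 25 responses in 63 treated (39.7%), adding the undosed to the denominator gives 25/67 = 37.3% at 5%, 25/70 = 35.7% at 10% and 25/75 = 33.3% at 15%.

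**6. Clock.** With a median PFS of 11.6 months (Section 3.2.1, nivolumab plus ipilimumab, intermediate/poor risk) and an assumed exponential distribution, 7 days is 7/353 of the median. The share of PFS events in that gap is 1 − exp(−0.693 × 7/353) = 1.4%, or about 0.9 of 63 participants.

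**The case against.** The case against acting is substantial. The comparison is labelled descriptive, and the numerical go/no-go guidance is the single-arm Simon count, for which the treated set suits. Sections 7.2 and 9 require eligibility to be met and screening completed before randomisation. Section 5.1.3.1 requires an adequate biopsy before randomisation, and Appendix 2 has participants consent to all treatments for which they are eligible. Each of these makes loss after allocation less likely. Section 10.3 promises a separate SAP and Section 10 lets sub-protocols add statistical detail, so a randomised-set analysis may yet appear. Undosed participants have only 30-day SAE collection specified, so they add little to a hazard ratio. All of this stands. It limits the likely size of the problem but does not remove it: a wide interval does not correct a bias, and Section 10.3 does not commit the SAP to this analysis.

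Three stronger readings are tempting but unsupported.
- **That allocation is known at least 5-7 days ahead.** Table 2-1 makes 5-7 days a ceiling, and the Synopsis describes randomisation at Day 1, Week 1.
- **That arm-specific checks remove participants after allocation.** Section 6 says "For entry into a study treatment per a FRACTION-RCC Sub-Protocol, additional treatment-specific criteria, if applicable, must also be met", but not that these criteria are first checked after allocation. The remark "To allow patients to complete all the post randomization procedures required for a sub-protocol" is a rationale in the change history (Appendix 9); current Table 2-1 mentions only a study-related test.
- **That scoring undosed participants as non-responders measures the bias.** With 45% ORR among the dosed, 0.45 × (63 − k)/63 for k = 2 to 8 gives 43.6% to 39.3%, a fall of 1.4 to 5.7 points. That is the effect of the scoring rule under assumed counts. It also treats 63 as the number randomised, whereas Section 5.2 gives 63 as the number treated.

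**Conclusion.** The point holds as a possibility of bias in a descriptive comparison; bias is not shown. The between-arm analysis excludes participants after open-label allocation, and a defined Randomized population stands unused for efficacy. The direction cannot be predicted. The size rests on an undosed rate that the documents do not give: about −2 to +1 ORR points for 2-5% loss in the control arm only, and about −7 to +4 for 10-15%, assuming a 40% ORR in both arms and 0-60% among the undosed. Both ranges are well inside the half-width of about 17 points. The first-dose clock alone matters little if the gap stays near a week. Nothing here affects the Simon evaluation. This is a cheap improvement to the ORR comparison, with a smaller gain for PFS and OS.

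**What to change.** In Section 10.3.1 and the SAP:

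1. Keep the treated population for the single-arm Simon evaluation and for the ORR endpoint in Section 4.
2. For the Track 1 between-arm comparison, estimate the ORR odds ratio and difference on all randomised Track 1 participants by first assigned arm, counting undosed participants as non-responders. Show the treated-set result beside it.
3. Report by arm, with reasons, the number randomised but not dosed and the number re-enrolled and re-randomised.
4. Give the PFS and OS hazard ratios from the randomisation date by assigned arm as a supportive analysis. Censor undosed participants at last contact, and state that little follow-up is specified for them.

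**Cost.** The ORR part needs no new data, since Section 7.2 already provides the randomisation schedules to the sponsor. It adds a little analysis and dilutes the ORR difference slightly: with 5% undosed in both arms and undosed participants of average prognosis, a 10-point difference becomes 10 × 0.95 = 9.5 points. If the loss is one-sided, non-responder scoring moves the difference itself, as the last column of the working table shows; the counts in item 3 let the reader judge this. The PFS and OS part adds little information, and new data collection is not realistic because Amendment 07 reports one participant left, on safety follow-up.
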